## 8.4 Expedited Adverse Event Reporting Requirements

### Expedited Adverse Event Reporting to DAIDS

The expedited adverse event (EAE) reporting requirements and definitions for this study and the methods for expedited reporting of adverse events (AEs) to the DAIDS Regulatory Compliance Center (RCC) Safety Office are defined in “The Manual for Expedited Reporting of Adverse Events to DAIDS” (DAIDS EAE Manual), **dated May 6, 2004**. The DAIDS EAE Manual is available on the RCC website: <http://rcc.tech-res-intl.com/>.

AEs reported on an expedited basis must be documented on the DAIDS Expedited Adverse Event Reporting Form (EAE Reporting Form) available on the RCC website: <http://rcc.tech-res-intl.com>. DAIDS EAE forms should be submitted to DAIDS through the Regulatory Compliance Center (RCC) Safety Office ([[contact]](mailto:[contact])) or call [name] or [contact] or [contact] or [contact].

### EAE Reporting Requirements for this Study

#### EAE Reporting Level

This study uses the Intensive Level of expedited AE reporting as defined in the DAIDS EAE Manual.

#### Study Agents for Expedited Reporting to DAIDS

The study agents that must be considered in determining relationships of AEs requiring expedited reporting to DAIDS are the tenofovir 1% vaginal gel and study gel applicator.

#### Grading Severity of Events

The Division of AIDS Table for Grading the Severity of Adult and Pediatric Adverse Events (DAIDS AE Grading Table), Version 1.0, December, 2004 and the Protocol Specific Toxicity Table must be used. The DAIDS AE Grading Table is available on the RCC website at <http://rcc.tech-res-intl.com/>.

#### EAE Reporting Periods

AEs must be reported on an expedited basis at the Intensive Level during the Protocol-defined EAE Reporting Period, which is the entire study duration for an individual subject (from study enrollment until study termination).

After the end of the Protocol-defined EAE Reporting Period stated above, the study site must report serious, unexpected, clinical suspected adverse drug reactions if the study site staff becomes aware of the event on a passive basis, i.e., from publicly available information.

## **8.5 Local Regulatory Requirements**

Site investigators will submit AE information in accordance with local regulatory agencies' or other local authorities' requirements. This reporting will include site IRB-mandated reporting of AEs, SAEs, and other relevant safety information.

## **8.6 Social Harms Reporting**

Although social harms are not expected in this study, the study site will make every effort to protect participant privacy and confidentiality, it is possible that participants' involvement in the study could become known to others, and that social harms may result. Social harms that are judged by the Investigator of Record to be serious or unexpected will be reported to the responsible site IRB at least annually, or according to their individual requirements. In the event that a participant reports social harm, every effort will be made by study staff to provide appropriate care and counseling to the participant, and/or referral to appropriate resources for the safety of the participant as needed.

# **9 CLINICAL MANAGEMENT**

## **9.1 Toxicity Management**

Based on results from previous clinical trials, significant toxicity in study participants is not expected in this trial of a single dose administration with minimal expected systemic absorption of this vaginal gel product. Lactic acidosis and severe hepatomegaly with steatosis, including fatal cases have been reported with the use of orally administered nucleoside analogs alone or in combination with other antiretrovirals. A majority of these cases have been in women. Obesity and prolonged nucleoside exposure may be risk factors. Particular caution is advised when administering nucleotide analogs to any patient with known risk factors for liver disease; however, cases have also been reported in patients with no known risk factors.

In the event of an expedited adverse event that occurs at the study site and that is judged to be definitely, probably, possibly, or probably not related to the study gel or applicator, product exposure will be minimized to the extent possible via cervicovaginal lavage (if clinically appropriate) and suspected toxicity will be managed according to Site SOPs by a physician on the study team at the discretion of the site investigator. Unless the participant withdraws her consent, she will remain in the study to complete all non-product related evaluations unless clinically contraindicated according to Appendix I.

## **9.2 Criteria for Withholding Study Product**

Participants may decline administration of study product. Physician investigators may decide not to administer study product to participants to protect their safety.

The withholding of study product will occur only under certain criteria. The criteria for an individual participant are:

- Request by participant to not receive study product
- Decision by the principal investigator to protect the participant's safety and/or if the participant is unable or unwilling to comply with study procedures

At least one of the above criteria must be met for the participant to not receive study product.

## **9.3 Criteria for Early Termination of Study Participation**

Participants may voluntarily withdraw from the study for any reason at any time. The principal investigators may, with the approval of the PSRT, withdraw participants to protect their safety, and/or if participants are unable or unwilling to comply with study procedures.

Early (premature) termination of study participants will occur only under certain criteria. The criteria for early termination from the study for an individual participant are:

- Request by participant to withdraw
- Request by the principal investigator to protect the participant's safety and/or if the participant is unable or unwilling to comply with study procedures

At least one of the above criteria must be met for the participant to be terminated early from the study.

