### **6.5.1 Prohibited Medications and Practices**

Vaginal douching will not be permitted to protect the integrity of the lower genital tract and reduce the possibility of adverse events due to agents other than the study products. However, in the event that prohibited practices are reported following

administration of study gel, the protocol-specified visit schedule will continue for such participants for safety assessment through study exit. All concomitant medications will be recorded on Concomitant Medication Records.

Vaginal, anal, and receptive oral sex will not be permitted for at least two weeks following gel administration. Women will be advised to follow the instructions of their surgeon.

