### **8.3 Adverse Events Definitions and Reporting Requirements**

#### **8.3.1 Adverse Events**

An AE is defined as any untoward medical occurrence in a clinical research participant administered an investigational product and which does not necessarily have a causal relationship with the investigational product. As such, an AE can be an unfavorable or unintended sign (including an abnormal laboratory finding, for example), symptom or disease temporally associated with the use of an investigational product, whether or not considered related to the product. The term “investigational product” for this study refers to tenofovir gel.

Study participants will be instructed to contact the study site staff to report any AEs they may experience, except for life-threatening events, for which they will be instructed to seek immediate emergency care. Where feasible and medically appropriate, participants will be encouraged to seek medical care where the study clinician is based, and to request that the clinician be contacted upon their arrival. With appropriate permission of the participant, and whenever possible, records from all non-study medical providers related to AEs will be obtained and required data elements will be recorded on study case report forms. All participants reporting an AE (including pelvic exam abnormalities) will be followed clinically until the AE resolves (returns to baseline) or stabilizes.

Study site staff will document on study CRFs all AEs reported by or observed in enrolled study participants from the time of enrollment until study termination, regardless of severity and presumed relationship to study product. The Protocol Specific Toxicity

Table (Appendix V) will be the primary tool for grading adverse events for this protocol, with the exception of asymptomatic bacterial vaginosis which will not be a reportable AE. Adverse events not included in that table will be graded by the DAIDS AE Grading Table Version 1.0, December 2004. In cases where an AE is covered in both tables, the Protocol Specific Toxicity Table will be the grading scale utilized.

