## **10.5 Participant Accrual, Follow-up, and Retention**

The accrual period will be 18 months. The study site will recruit and enroll a total of 16 participants. Each participant will be followed for two weeks following gel administration. Once a participant has enrolled in the study, the study site will make every reasonable effort to retain her for the entire study period.

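### Section 9.3 allows a woman already given the single dose to be terminated for non-compliance, and recording of new adverse events then stops before the Two Week Phone Call

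*Protocol*

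**What the plan says.** Section 9.3 of the protocol gives the investigator a discretionary power, subject to PSRT approval, to "withdraw participants to protect their safety, and/or if participants are unable or unwilling to comply with study procedures". The list of formal criteria that follows repeats the ground, "Request by the principal investigator to protect the participant's safety and/or if the participant is unable or unwilling to comply with study procedures", without repeating the PSRT approval. Neither sentence refers to whether gel has been given, and neither asks for any safety contact after termination.

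Two recording windows close at termination. Under 8.3.1, adverse events go on CRFs "from the time of enrollment until study termination, regardless of severity and presumed relationship to study product". Under 8.4 (EAE Reporting Periods), the expedited period is "the entire study duration for an individual subject (from study enrollment until study termination". After that period, serious and unexpected suspected drug reactions are still to be reported, but only if the site learns of them passively.

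Other sections keep women under observation. Section 9.1 covers an expedited event that occurs at the site and is judged anything from definitely related to probably not related. The woman then stays in the study for her remaining non-product evaluations unless she withdraws consent or they are clinically contraindicated. Section 6.5.1 says that after a prohibited practice "the protocol-specified visit schedule will continue for such participants for safety assessment through study exit". Section 8.3.1 has reported adverse events followed clinically until they resolve or stabilize.

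**The concern.** The product is one dose given at Time 0 (6.1). Before gel, excluding a woman who cannot or will not follow procedures prevents an exposure, and section 9.2 already provides for that. After gel, ending participation on the same ground prevents no further dose. All it can change is how long she is observed.

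Inability to comply is also not a neutral reason in this population. Every participant is scheduled for a cesarean section about two hours after gel, and a woman with a surgical or postpartum complication is among those least able to give timed draws or take a call. Loss of later follow-up could therefore be related to the outcome being described.

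What is at stake is completeness of the two-week record behind the secondary objective on systemic safety, in what section 2.2 describes as the first study of a candidate microbicide in pregnant women. With 16 women, one later event is a visible part of that record.

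**Working it through.** The protocol states no figure for this point, so the check is mainly a reading of sections against each other.

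**1. Can a dosed woman be terminated for non-compliance?** Yes. Section 9.3 is not limited to the time before gel, and section 9.2 separately uses the same ground to withhold gel. PSRT approval is required by the first paragraph of 9.3.

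**2. What stops at termination?** CRF recording of adverse events (8.3.1) and active expedited reporting (8.4). The planned contacts after Day 0 are the 24 Hour Evaluation (22 to 26 hours) and the Two Week Phone Call (target Day 14, window Day 10 to 18). For a woman terminated on Day 1, the unobserved stretch to the target call is 14 − 1 = 13 days (9 to 17 days across the window).

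**3. What does not stop?**
- Events recorded before termination. They are collected at each PK time point and at 24 hours, and nothing in 9.3 removes them.
- Clinical follow-up of a reported event (8.3.1), although no CRF recording is required after termination.
- Passive reporting of serious, unexpected suspected reactions (8.4).

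What can be lost is a new event, or the later outcome of a known one.

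**4. Does 9.1 close the gap?** In part. It covers expedited events at the site in every relatedness category except not related. Events judged not related, non-expedited events and off-site events fall outside it. Where it does apply, 9.1 lets her leave only by withdrawing consent (or omit evaluations that are clinically contraindicated), whereas 9.3 lets the investigator, with PSRT approval, end her participation. The protocol does not say which governs.

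**5. Scale.** No early-termination rate is given, so frequency cannot be estimated. The illustration assumes 16 dosed women and exactly one event, arising after termination of the woman concerned. Two-sided exact (Clopper-Pearson) 95% limits are:
- Lower, x events in n: the 2.5% quantile of Beta(x, n − x + 1).
- Upper: the 97.5% quantile of Beta(x + 1, n − x).
- Zero events: lower limit 0, upper limit 1 − 0.025^(1/n).

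| Record | Estimate | Exact 95% CI |
|---|---|---|
| Event captured, 1/16 | 6.3% | 0.2% to 30.2% |
| Event missed, 0/16 | 0% | 0% to 20.6% |

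For 0/16 the upper limit is 1 − 0.025^(1/16) = 20.59%. Section 10.4 prints upper bounds of 20% and 30% for 0 and 1 of 16 in the absorption setting. These are the same limits, with 20.59% cut to 20%.

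**The case against.** The strongest reply is that the protocol already contains most of the protection needed. Termination is discretionary and needs PSRT approval, and the PSRT is the safety review body. A complication that makes a woman unable to comply arises before termination, so it is already on the CRF and inside the expedited period. Section 9.1 holds on to the women whose events are most likely to bear on the gel. Final contact may be made at the site or in the community (7.7). All of this stands, and it makes the gap small.

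A reader might also infer more than the text supports:
- **That the complication itself disappears from the safety data.** It does not. Only later events and outcomes are exposed.
- **That the investigator can act alone.** The criteria list omits PSRT approval, but the paragraph above it requires it.
- **That all expedited reporting ceases.** The passive route remains, though it is narrow.
- **That a terminated woman leaves the denominator, giving 0/15 (upper limit 21.8%).** No section drops her, and analysis sets may be defined in an analysis plan that is not shown.
- **That 9.3 contradicts section 10.5.** That section says "the study site will make every reasonable effort to retain her for the entire study period". This is a best-effort clause and can stand beside a permissive termination rule.
- **That 9.3 contradicts 6.5.1.** Section 6.5.1 covers prohibited practices only. It shows a different approach to non-compliance after dosing, not a direct conflict.

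What the reply does not meet is that nothing in 9.3 requires safety recording to continue in a dosed woman, and that 9.1 and 9.3 give different answers for some of the same women.

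**Conclusion.** The point holds in a limited form. For a woman who has received gel, termination for non-compliance under 9.3 ends CRF recording and active expedited reporting and avoids no further dose. New events or outcomes up to the Two Week Phone Call can then be missed, mainly where the event is judged not related, is not expedited or occurs off site. For on-site expedited events in the other relatedness categories, 9.1 and 9.3 conflict and must be reconciled.

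The number of women affected is unknown and may be zero. A bias of any given size is therefore not shown. The change from 1/16 to 0/16 is an illustration that assumes one later event in one terminated woman who stays in the denominator. This is an inexpensive improvement in data capture for a descriptive secondary objective. It does not affect the pharmacokinetic objective or the sample size.

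**What to change.** Add to section 9.3 that, for a woman who has received gel, individual study procedures such as draws and specimens may be stopped. Adverse event and expedited recording, the 24-hour chart review and the Two Week Phone Call then continue unless she withdraws consent, and she stays in the safety denominator. Repeat the PSRT approval in the criteria list so that both parts of 9.3 agree.

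Reconcile 9.3 with 9.1, stating which applies when both could, and make the end of the windows in 8.3.1 and 8.4 match. The addition concerns observation and recording only. It leaves clinical management, including any clinical reason not to perform an evaluation, as the sponsor sets it.

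The cost is a few lines of text, plus one chart review and one phone call for each affected woman.

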# **10 STATISTICAL CONSIDERATIONS**

## **10.1 Overview and General Design**

This is a single-dose, single-site, open label study. All the enrolled women will be administered tenofovir 1% vaginal gel. The planned total length of follow-up is 2 weeks.

## **10.2 Study Major Endpoints**

Consistent with the primary and secondary study objectives, the following endpoints will be assessed:

- Maternal 3rd trimester pharmacokinetic measures: AUC, Cmax
- Endometrial tenofovir levels
- Placental transfer : cord blood tenofovir levels, placental tissue tenofovir levels, and amniotic fluid tenofovir levels

### 10.3 Study Hypothesis

We hypothesize:

- Study hypothesis 1: Plasma absorption in participants will be detectable in a percentage of women similar to that seen in HPTN 050 (approximately 33%)
- Study hypothesis 2: Of women with detectable levels of tenofovir, a small fraction will have detectable levels in endometrium, cord blood, placental tissue, and amniotic fluid

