HPTN 050 also addressed pharmacokinetics of vaginally administered tenofovir gel. Fourteen of 25 women (56%) with pharmacokinetic results had low, but detectable, serum tenofovir levels (limit of quantitation: 3.0 ng/mL) at some point in the 12 hours after dosing on either Day 0 (following the first dose) or on Day 13 (after daily dosing); three of the 14 had detectable levels on both days. The maximum tenofovir concentrations ( $C_{max}$ ) ranged from 3.0 - 25.8 ng/mL, with no clear dose-concentration relationship identified. For the woman with the 25.8 ng/mL level, this peak level occurred two hours following the dose; the level rapidly declined to 10.9 ng/mL at four hours and was undetectable at 12 hours following the dose. Besides the outlier with the highest tenofovir level, the next highest  $C_{max}$  was 7.1 ng/mL. Considering all women in the PK cohort, the median tenofovir  $C_{max}$  was 3.4 ng/mL (interquartile range: below limit of quantitation [3.0 ng/mL] to 4.7 ng/mL). The median  $C_{max}$  for all subjects (3.4 ng/mL) corresponds to approximately 1% of the maximum ( $C_{max, steady-state (ss)}$ ) and 7% of the minimum (C24 single dose) blood concentrations at steady-state with 300 mg daily oral tenofovir dosing. Findings from CONRAD A04-095 are expected to further inform the pharmacokinetic data on vaginally administered tenofovir gel.

Figure 1 presented below demonstrates tenofovir blood concentration following vaginal administration of tenofovir 1% gel in HPTN 050. All levels for all women with measurable tenofovir levels in the blood are shown. (14 of 25; lower limit of quantitation (LLOQ) approximately 3.0 ng/mL [dotted line]). Legend indicates “cohort” – “ID” – “study day”. For reference the tenofovir level associated with the median 24 hour post-dose blood concentration following an oral 300 mg tenofovir dose is indicated with dashed line.

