## **6 STUDY PRODUCT**

### **6.1 Regimen**

All study participants will receive a single vaginal dose of 4 grams of tenofovir 1% gel followed by 24 hours of intensive PK sampling.

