### 10.4 Sample Size

The power of the study can be characterized as follows: if the overall absorption rate (defined as the proportion of women with detectable levels of PMPA in plasma, endometrium, cord blood, placental tissue, and/or amniotic fluid) was expected to be 33%, 16 women would provide 72% power to exclude absorption rate > 60%. In addition, the lower and upper bounds of the exact 95% confidence interval (CI) around the absorption rate are 13% and 57%, respectively, if the observed number of absorption in a cohort of 16 women was 5 (31%: 5 out 16).

For endpoints where no or very low absorption rates are expected (e.g., endometrium, cord blood, placental tissue, and amniotic fluid), 16 women would provide 80% power to exclude absorption rate > 25% assuming the true rate of absorption is 5%. In addition, the upper bounds of the exact 95% confidence interval (CI) around the absorption rate are 20% and 30% if the observed number of absorption in a cohort of 16 women was 0 or 1, respectively.

Additional participants may enroll in the study, at the discretion of the protocol team, to replace currently enrolled participants who receive study gel but whose time of cesarean delivery is greater than 8 hours following the time of study gel administration. Thus, in the event that participants are replaced for this purpose, the total sample size at the end of the study may slightly exceed 16 participants who received study gel.

A sample size of 16 women is insufficient to provide a formal statistical assessment for the comparison between the plasma absorption level observed in HPTN 050 and the one that will be observed in this study.

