### **13.3 Risk Benefit Statement**

#### **13.3.1 Risks**

Phlebotomy may lead to discomfort, feelings of dizziness or faintness, and/or bruising, swelling and/or infection. Pelvic examination may cause mild discomfort and/or vaginal bleeding or spotting. Participation in clinical research includes the risks of loss of confidentiality and discomfort with personal nature of questions.

Waiting for test results may lead to anxiety in participants. Disclosure of STI status may cause sadness or depression in participants. Disclosure of HIV-positive status has been associated with depression, suicidal ideation, and denial, as well as social isolation.

Some of the possible side effects of the study gel are dryness, itching, burning, or pain in the genital area. Administration of tenofovir gel intravaginally at 0.3% and 1% concentrations in the HPTN 050 Phase I study resulted in minimal local irritation and little or no systemic adverse effects were identified. Although 92% of participants reported at least one AE, 87% of those reported AEs were mild, and 77% of the AEs were limited to the genitourinary tract. Four severe AEs were reported, with only one, lower abdominal pain, thought to be product-related. The risks associated with tenofovir gel are believed to be less than those identified for systemic use. In the HPTN 050 Phase I study of tenofovir gel, PK analysis in a subset of participants demonstrated that there is no clinically significant systemic toxicity. Fourteen of 25 women with PK results had low, but detectable, tenofovir levels.

The most common AEs in patients receiving TDF with other antiretroviral (ARV) therapy in clinical trials were mild to moderate gastrointestinal events, such as nausea, diarrhea, vomiting, and flatulence. Less than 1% of patients discontinued participation in the clinical studies because of gastrointestinal AEs. Laboratory abnormalities observed in studies occurred with similar frequency in the TDF and placebo-treated groups.

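### The 33% detection rate attributed to HPTN 050 is unsourced, does not match the 14 of 25 women (56%) the protocol reports from that study, and carries the power claim in 10.4

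*Protocol*

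**What the plan says.** Hypothesis 1, given in Protocol 2.11 and repeated in 10.3, is: "Plasma absorption in participants will be detectable in a percentage of women similar to that seen in HPTN 050 (approximately 33" per cent). Neither section says where the 33% comes from.

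Section 2.10 reports the HPTN 050 result: "Fourteen of 25 women (56%) with pharmacokinetic results had low, but detectable, serum tenofovir levels". These women were detectable "on either Day 0 (following the first dose) or on Day 13 (after daily dosing"), and "three of the 14 had detectable levels on both days". Section 13.3.1 repeats the count: "Fourteen of 25 women with PK results had low, but detectable, tenofovir levels".

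The present trial has one dose and one sampling occasion (6.1): "All study participants will receive a single vaginal dose of 4 grams of tenofovir 1% gel followed by 24 hours of intensive PK sampling".

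Section 10.4 uses 33% as the planning rate. The overall absorption rate is "defined as the proportion of women with detectable levels of PMPA in plasma, endometrium, cord blood, placental tissue, and/or amniotic fluid", and the power statement supposes that this rate "was expected to be 33%, 16 women would provide 72% power to exclude absorption rate > 60" per cent. Section 10.6.2 plans exact 95% Clopper-Pearson intervals for proportions detectable.

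**The concern.** The hypothesis speaks of a percentage of women and names HPTN 050 as its source, yet the protocol's own HPTN 050 percentage of women is 56%. Nothing in the document connects the two numbers.

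The 33% does two jobs. It is the reference for hypothesis 1, and comparison with recent historic controls is a secondary objective (3.2). It is also the assumed truth behind the only power statement that covers plasma. Suppose 9 of 16 women (56%) were detectable. That would equal the percentage of women cited from HPTN 050, yet set against the stated benchmark it would read as nearly double. And if the true rate is well above 33%, the design has little chance of excluding 60%.

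Section 10.4 also applies the 33% to detection in any of five matrices, whereas 10.3 applies it to plasma alone. The text does not say whether the two rates are meant to be the same.

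**Working it through.** **Inputs.** From 2.10: 25 women with pharmacokinetic results, 14 detectable on either day, 3 of them on both. From 10.4: n = 16, planning rate 33%, rate to exclude 60%, stated power 72%. The one-sided 5% level below is an assumption, since 10.4 gives no alpha or method.

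**1. What the HPTN 050 counts allow**
- Women detectable on either day: 14/25 = 56%.
- Positive woman-days: 14 + 3 = 17. If all 25 women were sampled on both days, 17/(25 × 2) = 34%.
- Day 0 alone, the single-dose comparator, is not reported. At least the 3 women positive on both days were positive on Day 0, and at most all 14 were. The range is 3/25 to 14/25, or 12% to 56%.

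So 33% agrees with a per-occasion reading and not with the reported percentage of women.

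**2. Reproducing the stated 72%**

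Normal approximation: power = Φ{[p0 − p1 − 1.645·√(p0(1−p0)/n)] / √(p1(1−p1)/n)}

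With p0 = 0.60, p1 = 0.33 and n = 16:
- √(0.60 × 0.40/16) = 0.1225, and 1.645 × 0.1225 = 0.2015
- √(0.33 × 0.67/16) = 0.1176
- (0.27 − 0.2015)/0.1176 = 0.583, and Φ(0.583) = 72.0%

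This matches the protocol.

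**3. The planned exact interval**

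The upper two-sided 95% Clopper-Pearson limit is 58.7% for 5/16 and 64.6% for 6/16. A rate above 60% is therefore excluded only when 5 or fewer women are detectable, and power is P(X ≤ 5 | 16, p).

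**4. Power across the range**

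| True rate | Normal approximation, one-sided 5% | Exact rule, X ≤ 5 |
|---|---|---|
| 33% | 72.0% | 55.8% |
| 34% | 68.9% | 52.4% |
| 45% | 33.9% | 19.8% |
| 50% | 20.8% | 10.5% |
| 56% | 9.7% | 4.1% |

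Comparisons should stay within a column: 72% falls to 10%, or 56% falls to 4%. Setting the exact 4% beside the stated 72% would mix a change of rule with a change of rate.

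**The case against.** A reader might infer that 33% flatly contradicts 56%, so that 33% is wrong and 56% is right. The documents do not support this. The 56% accumulates over two occasions, one of them after daily dosing, while this trial has a single dose and one occasion. The per-occasion 34% is close to 33% and may well be its source. That part of the objection stands. It does not cure the wording: a share of woman-days is not a percentage of women, it pools first-dose with repeat-dose data, and the reader has to guess it.

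The median Cmax in 2.10 (3.4 ng/mL against a limit of 3.0) might look like separate evidence for a rate above one half. Section 2.10 does not split it by day. If it is pooled over both days, it only restates the either-day count and says nothing about a single dose.

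A reader might also inflate 33% for the four further matrices in 10.4, treating each as independently detectable. Hypothesis 2 works against this, because it treats tissue-positive women as a fraction of those with detectable levels. On that model the any-matrix rate equals the plasma rate. The any-matrix rate cannot be lower than the plasma rate, but the protocol gives no ground for a specific higher figure. The definition still needs stating.

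The more sensitive assay (7.9.2) is a fair reason to think 33% could be low. The protocol says only that it may raise the number of quantifiable samples, and gives no size.

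Finally, 10.4 disclaims a formal comparison with HPTN 050 and 10.6.2 is descriptive. The exact 95% interval for 9/16 is 30% to 80%, which includes 33%, so such a result would not establish raised absorption. This limits the consequence and is accepted.

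**Conclusion.** The point holds as an unsourced benchmark that does not match the reported percentage of women, with a power claim resting on it. It is not a proven arithmetic error, and the documents do not show that 56% is the correct single-dose rate.

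Over true rates of 33% to 56%, power to exclude a rate above 60% runs from 72% down to 10% by the approximation behind the stated figure, and from 56% down to 4% by the planned exact interval. Even at 33%, the planned interval gives 56%, not 72%.

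Two assumptions matter: a one-sided 5% level for reproducing the 72%, and sampling of all 25 women on both days for the 34%. No hypothesis test or decision rule depends on the 33%.

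**What to change.** - **2.11 and 10.3:** give the HPTN 050 numerator, denominator and dosing day behind the benchmark. Day 0 is preferable as the single-dose comparator; its count is not in the protocol and has to come from the HPTN 050 data. Note that 56% is cumulative over two occasions.
- **10.4, definition:** state whether the absorption rate is plasma only or any matrix. If any matrix, say that it is taken as equal to the plasma rate under hypothesis 2, or justify another value.
- **10.4, power:** replace the single 72% with exact power under the planned Clopper-Pearson rule (5 or fewer of 16): 56% at 33%, 20% at 45% and 4% at 56%. Do not claim that the design can exclude a rate above 60% if the planning rate is near 56%.

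The cost is protocol wording and a three-row table, with no change to design or sample size. The stated power becomes less favourable.
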